## **4. STUDY DRUG**

### **4.1 Description of SYNT001**

SYNT001 is provided in vials containing 5 mL SYNT001 (extractable volume) at a nominal concentration of 50 mg/mL. The product is supplied as a liquid at pH  $6.5 \pm 0.5$ . SYNT001 is diluted in dextrose 5% in water (D5W) to prepare the solution for infusion. SYNT001 will be infused via IV in 250 mL over 1 hour  $\pm$  15 minutes using a 0.2-micron, inline filter.

For detailed information regarding SYNT001 preparation and administration, refer to the Pharmacy Manual.

### **4.2 Dose Requirements**

The specification for host cell deoxyribonucleic acid (DNA) in SYNT001 is  $<2$  pg/mg, the limit of quantitation of the assay. To comply with regulatory guidelines, which specify a maximum level of 10 ng host cell DNA per dose, dosing per subject is limited to 5000 mg SYNT001.

For example, a subject with a body weight of 166 kg and enrolled in the  $\leq 30$  mg/kg dose cohort will receive  $\leq 4960$  mg SYNT001 per dose. If a subject's body weight extrapolates to an expected dose  $\geq 5000$  mg SYNT001, the dose will be capped to ensure the 5000 mg SYNT001 per dose limit is not exceeded.

A subject with a body weight of 111 kg and enrolled in the  $\leq 45$  mg/kg dose cohort will receive  $\leq 4995$  mg SYNT001 per dose. If a subject's body weight extrapolates to an expected dose  $\geq 5000$  mg SYNT001, the dose will be capped to ensure the 5000 mg SYNT001 per dose limit is not exceeded.

### **4.3 Handling and Storage of SYNT001**

All supplies of SYNT001 will be provided by the Sponsor and must be stored refrigerated ( $2^{\circ}\text{C}$  to  $8^{\circ}\text{C}/36^{\circ}\text{F}$  to  $46^{\circ}\text{F}$ ) in the carton and protected from light, in a securely locked area, accessible to authorized persons only, until needed for dose preparation.

### **4.4 Study Drug Accountability**

The Investigator (or designee) is responsible for maintaining accurate accountability records of the study drug throughout the clinical study. Qualified site personnel will inventory the study drug received and will maintain records of disposition of the drug, including dates, quantity and use. All study drug received at the site must be accounted for on an accountability log provided by the Sponsor. All dispensing and accountability records will be available for Sponsor review. Study drug accountability will be verified during on-site monitoring visits.

Upon the completion or termination of the study, and upon written authorization from the Sponsor, or its representative, all unused and/or partially used study drug should be returned or destroyed at the investigational site, as specified by Sponsor. It is the Investigator's responsibility to ensure that the Sponsor, or its representative, has provided written authorization that procedures for proper disposal of the study drug have been established, and that appropriate

records of the disposal are documented and maintained. No unused study drug may be disposed of until fully accounted for by the Sponsor monitor (or designee).

## 5. STUDY DESIGN

### 5.1 Study Sites

This study will be conducted at approximately 10 global study sites.

### 5.2 Overview of Study Design

This is a multicenter, open-label safety study to determine the dose regimen of SYNT001 administered intravenously in subjects with pemphigus (vulgaris or foliaceus). Approximately 20 (up to a maximum of 32) eligible subjects will receive planned doses of 10 mg/kg up to 45 mg/kg of SYNT001.

Cohorts will be dosed sequentially beginning with Cohort 1. Up to 8 eligible subjects will be enrolled in Cohort 1 and will receive 5 once-weekly 60-minute infusions of SYNT001 10 mg/kg. Based on review of safety, PD, and clinical outcomes of Cohort 1, sequential cohorts will enroll, pending recommendation received from a scheduled Dose Escalation Committee (DEC) review.

The DEC will consist of the Medical Monitor, an Independent Clinical Expert and a Syntimmune Medical Officer. To assist in the safety assessments, the DEC may request that Investigators, other experts, or members within their organization review the data and participate in the discussions.

Each cohort must be fully enrolled before a successive cohort will be opened for enrollment. An overview of the study cohorts is provided in Table 5 and Figure 1 shows a schematic of the study design.

**Table 5. Cohort Overview**

Cohort No.	No. of Subjects	SYNT001 Dose	No. of Doses	DEC Review Timepoint
1 a	up to 8	10 mg/kg	5	NA
2 b	4 c	≤30 mg/kg d	5	When 100% of Cohort 1 subjects reach Day 42
3 b	4 c	≤30 mg/kg d	14	When 50% of Cohort 2 subjects reach Day 42
4 b (optional)	4 c	≤45 mg/kg d	≤14	When 50% of Cohort 3 subjects reach Day 42 e

Abbreviations: DEC = Dose Escalation Committee; NA = not applicable

- No more than 3 subjects with pemphigus foliaceus may be enrolled
- Two or fewer subjects with pemphigus foliaceus may be enrolled
- Up to 4 additional subjects may be added following DEC's evaluation.
- Dose will be recommended by the DEC and will be based on both an ongoing and set timepoint review of safety and pharmacodynamic evaluations including but not limited to, dose-limiting toxicities (DLTs), adverse events (AEs), treatment-emergent adverse events (TEAEs), serious adverse events (SAEs), and total IgG levels.
- All available data will be considered.

The first 2 subjects in Cohorts 1 and 2 will be enrolled at staggered intervals to facilitate adequate safety evaluation before dosing of subsequent subjects may proceed. A staggered

dosing interval for the first 2 subjects enrolled in successive cohorts will not be required if the planned dose is equal to or lower than that previously administered.

At 24-hour and 7-day intervals described below, the DEC will review of all available safety data (including but not limited to dose limiting toxicities [DLTs], AEs, TEAEs, and SAEs, PD (including but not limited to IgG levels), and clinical outcomes.

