4 b (optional)	4 c	≤45 mg/kg d	≤14	When 50% of Cohort 3 subjects reach Day 42 e

Abbreviations: DEC = Dose Escalation Committee; NA = not applicable

- No more than 3 subjects with pemphigus foliaceus may be enrolled
- Two or fewer subjects with pemphigus foliaceus may be enrolled
- Up to 4 additional subjects may be added following DEC's evaluation.
- Dose will be recommended by the DEC and will be based on both an ongoing and set timepoint review of safety and pharmacodynamic evaluations including but not limited to, dose-limiting toxicities (DLTs), adverse events (AEs), treatment-emergent adverse events (TEAEs), serious adverse events (SAEs), and total IgG levels.
- All available data will be considered.

The first 2 subjects in Cohorts 1 and 2 will be enrolled at staggered intervals to facilitate adequate safety evaluation before dosing of subsequent subjects may proceed. A staggered dosing interval for the first 2 subjects enrolled in successive cohorts will not be required if the planned dose is equal to or lower than that previously administered.

At 24-hour and 7-day intervals described below, the DEC will review all available safety data (including but not limited to dose limiting toxicities [DLTs], AEs, TEAEs, and SAEs, PD (including but not limited to total IgG levels), and clinical outcomes.

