**DEC Safety Review of 24-hour Data for Cohorts 1 and 2, Subject 1**

- The first 2 subjects will be dosed at least 24 hours apart. A DEC review of the 24-hour safety data for the first subject will be performed to ensure that there are no overt safety concerns before dosing the second subject.

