**DEC Safety Review of 7-day Data for Cohorts 1 and 2, Subjects 1 and 2**

- The 7-day safety data for the first 2 subjects will be performed prior to dosing the remaining subjects in the cohort.

The 24-hour and 7-day reviews will consider seriousness and severity of AEs/TEAEs/SAEs and relatedness to study drug, vital sign assessments, physical examinations, and clinical laboratory testing.

At scheduled reviews, the DEC may recommend increasing the number of subjects to be enrolled (from 4 up to 8 as shown in Table 1) and advise on the planned dose for each successive cohort. Further, the DEC may recommend pausing and resuming or halting enrollment.

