#### **DEC Safety Review of 24-hour Data for Cohorts 1 and 2, Subject 1**

The first 2 subjects will be dosed at least 24 hours apart. A DEC review of the 24-hour safety data for the first subject will be performed to ensure that there are no overt safety concerns before dosing the second subject.

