#### **Safety Review of 7-day Data for Cohorts 1 and 2, Subjects 1 and 2**

The 7-day safety data for the first 2 subjects will be performed prior to dosing the remaining subjects in the cohort.

The 24-hour and 7-day reviews will consider seriousness and severity of AEs/TEAEs/SAEs and relatedness to study drug, vital sign assessments, physical examinations, and clinical laboratory testing.

For further information about dose escalation and study stopping rules, refer to [Section 9.5.1](#) and [Section 9.5.2](#), respectively.

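### The waiver implies sentinel dosing for a later, higher-dose cohort, but the interval and both safety reviews are stated only for Cohorts 1 and 2

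*Protocol*

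**What the plan says.** Section 5.2, after Table 5, sets the positive rule: "The first 2 subjects in Cohorts 1 and 2 will be enrolled at staggered intervals to facilitate adequate safety evaluation". The next sentence deals with later cohorts and says of the stagger that this "dosing interval for the first 2 subjects enrolled in successive cohorts will not be required if the planned dose is equal to or lower", compared with doses already given.

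The detail follows under two headings:

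- "DEC Safety Review of 24-hour Data for Cohorts 1 and 2, Subject 1". The text beneath says "The first 2 subjects will be dosed at least 24 hours apart" and requires a DEC review of the first subject's 24-hour data before the second is dosed.
- "Safety Review of 7-day Data for Cohorts 1 and 2, Subjects 1 and 2". The text beneath requires the 7-day data on the first two subjects to be reviewed before anyone else in the cohort is dosed.

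The Synopsis repeats this structure, with its second heading reading "DEC Safety Review of 7-day Data for Cohorts 1 and 2, Subjects 1 and 2".

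Table 5 allows up to 30 mg/kg in Cohorts 2 and 3 and up to 45 mg/kg in optional Cohort 4. Its footnote says the dose of each cohort after the first is "based on both an ongoing and set timepoint review of safety and pharmacodynamic evaluations".

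**The concern.** The waiver is conditional on the dose not rising. That condition has a purpose only if the stagger is required when the dose does rise. The provisions that make a stagger work (how long to wait, who looks, and what must be reviewed before dosing continues) are nevertheless limited by their headings to Cohorts 1 and 2. A site opening Cohort 4 could conclude that a stagger of unspecified length applies, or that none does. With about 10 sites (Section 5.1), both readings could be acted on.

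The gap falls at the one step that goes above reported human doses. Section 10.3.2 says infusion-reaction symptoms can appear as late as 24 hours. Section 10.3.3 puts the single-dose IgG nadir at about 5 days. The 24-hour and 7-day reviews cover both windows; a stagger of unknown length need not. If the first Cohort 4 subjects are dosed close together, a reaction in subject 1 may become apparent only after the others have had their first infusion.

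**Working it through.** No sample size, power or error rate is involved, and the plan gives no figure to reproduce. The check compares the text on scope and then sets out the dose and timing arithmetic.

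**1. Which cohorts each provision covers**

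| Provision | Cohorts 1 and 2 | Later cohort, equal or lower dose | Later cohort, higher dose |
|---|---|---|---|
| Stagger of the first two subjects | Required | Waived | Implied only |
| Minimum interval | 24 hours | Not applicable | Not stated |
| DEC review before subject 2 | Required | Not applicable | Not stated |
| 7-day review before the rest | Required | Not applicable | Not stated |

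By heading, there are two review gates within each of Cohorts 1 and 2 and none within a higher-dose later cohort.

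**2. Whether another rule supplies the gate**

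- Pre-cohort DEC review (Table 5): takes place before anyone has received the new dose.
- Continuous DEC review (Table 5 footnote, Section 9.5.1) and the DEC's power to recommend a pause (Synopsis): neither makes the next subject's dosing wait for a completed review.
- Grade 3 rule (Section 9.5.1): needs clinically significant, drug-related events in at least two subjects.
- Grade 4 rule (Section 9.5.2): acts after a drug-related life-threatening event.
- Individual rule (Section 9.5.3): stops only the affected subject.

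None of these holds subject 2, or subjects 3 onward, until earlier data have been reviewed. A single related Grade 3 reaction in subject 1 would not, by rule, delay subject 2.

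**3. Which cohorts are affected**

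- Cohort 4: affected at any dose above that already given. At its cap, 45 / 30 = 1.5 times both the Cohort 2 and 3 cap and the highest single dose reported in healthy subjects (Section 2.2). The monkey no-adverse-effect level of 100 mg/kg is 100 / 45 = 2.2 times that cap.
- Cohort 3: affected only if Cohort 2 is dosed below 30 mg/kg and Cohort 3 goes higher. Its first infusion stays within the reported single-dose range.

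**4. What the pre-Cohort 4 review can rest on**

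The trigger is 50% of Cohort 3 at Day 42: 0.5 × 4 = 2 subjects, or 0.5 × 8 = 4 if the cohort is expanded. Infusions on Days 0, 7, 14, 21, 28 and 35 give 6 doses each, or 7 with the Day 42 infusion, all at 30 mg/kg or less. All available data are considered, but none are at the new dose.

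**5. Delay if the gates are applied**

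Subject 2 is dosed at the earliest 1 day after subject 1, and the 7-day data follow: 1 + 7 = 8 days before subject 3.

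**The case against.** The strongest reply is that this is loose drafting rather than a contradiction. No sentence exempts a higher-dose Cohort 4. The waiver uses the same terms as the rule for Cohorts 1 and 2. Neither the lead-in to the reviews nor the sentences under the headings name a cohort. The natural reading is that the same procedure carries over, with the headings naming the cohorts where the stagger is unconditional. That is probably the intent, and it keeps the point modest. It does not settle the text, because the headings limit the scope expressly.

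Two sources are not visible: the Figure 1 enrolment schematic and the DEC charter, to which the Synopsis refers for more on the committee's role. Either might show staggering by cohort. Even so, the headings sites work from would still say Cohorts 1 and 2.

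The DEC also controls the opening of each cohort, may recommend a pause and may look at data at any time. Cohort 3 must be fully enrolled before Cohort 4 opens, so more than two subjects may contribute data. Cohort 4 is optional, 45 mg/kg is a ceiling, and the monkey no-adverse-effect level comes from weekly dosing of up to 14 doses. All of this stands and lowers the risk, but none of it creates a required look between subjects.

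Finally, the waiver does not say where the earlier dose must have been given. Reading it as within this study would also stagger a Cohort 3 dosed above Cohort 2, at a level already given to healthy subjects. That is a choice, but it matches the protocol's own approach: Cohort 2 is staggered although its cap of 30 mg/kg was already given in the healthy-subject study.

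**Conclusion.** The inconsistency is real and should be fixed before any later cohort opens above the doses already given. As written, such a cohort has an implied stagger with no length and no required within-cohort review, against two review gates in each of Cohorts 1 and 2. The main case is optional Cohort 4, at up to 1.5 times the highest human dose the protocol reports.

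The conclusion concerns the protocol text alone. It rests on reading the conditional waiver as implying a stagger when the dose rises, and on the headings meaning what they say. It does not claim that the other safeguards are absent, or that the sponsor intends to omit sentinel dosing.

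**What to change.** Make the same edits in Section 5.2 and in the Synopsis, and keep the waiver for equal or lower doses.

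1. After the waiver sentence, add: *If a later cohort's planned dose is above the highest dose already given in this study, at least 24 hours must separate dosing of its first and second subjects, and the 24-hour and 7-day DEC reviews apply exactly as in Cohorts 1 and 2.*
2. In both review headings, extend the scope to *Cohorts 1 and 2 and any later cohort above the highest dose already given in this study*.

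The drafting cost is one sentence and two headings in each of two sections. If a higher-dose cohort opens, the operational cost is two short DEC reviews and about 8 days before the third and later subjects can be dosed. If no later cohort exceeds the earlier doses, there is no cost.

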#### **DEC Safety Review of 24-hour Data for Cohorts 1 and 2, Subject 1**

The first 2 subjects will be dosed at least 24 hours apart. A DEC review of the 24-hour safety data for the first subject will be performed to ensure that there are no overt safety concerns before dosing the second subject.

#### **Safety Review of 7-day Data for Cohorts 1 and 2, Subjects 1 and 2**

The 7-day safety data for the first 2 subjects will be performed prior to dosing the remaining subjects in the cohort.

The 24-hour and 7-day reviews will consider seriousness and severity of AEs/TEAEs/SAEs and relatedness to study drug, vital sign assessments, physical examinations, and clinical laboratory testing.

For further information about dose escalation and study stopping rules, refer to [Section 9.5.1](#) and [Section 9.5.2](#), respectively.

### **5.3 Randomization and Blinding**

This is an open-label study.

## 6. STUDY POPULATION

### 6.1 Target Population

This study will be conducted in approximately 20 male and female subjects aged 18 and older with a confirmed diagnosis of pemphigus (vulgaris or foliaceus).

Up to 8 subjects may be enrolled in Cohort 1. Four subjects will be enrolled sequentially in Cohort 2, 3, and 4 (optional cohort). An additional 4 subjects may be enrolled in Cohorts 2, 3 and 4 (optional cohort) following DEC's evaluation and recommendation.

Subjects who withdraw for any reason other than an AE and who do not receive study drug or have only received one dose of study drug may be replaced, up to one subject per cohort. Thus, the maximum number of subjects who may be enrolled in this study is 36 (20 + up to 12 additional subjects, + up to 4 replacements, as necessary).

Within Cohort 1, no more than 3 subjects may be enrolled with pemphigus foliaceus. Within successive cohorts,  $\leq 2$  subjects with pemphigus foliaceus may be enrolled.

Subjects will be enrolled only once in the study and will not be included in subsequent dosing cohorts. Subjects who do not receive all doses of study drug will continue to be followed through all scheduled visits.

### 6.2 Inclusion Criteria

A subject must meet the following criteria to be eligible for the study:

1. Willing and able to read, understand, and sign an informed consent form.
2. Male or female  $\geq 18$  years of age at the time of screening.
3. Documented diagnosis of pemphigus vulgaris or foliaceus based on all 3 of the following criteria:
  - a. Documented clinical history consistent with pemphigus vulgaris or foliaceus (clinical presentation defined as mucosal and/or skin lesions).
  - b. Presence of Anti-Dsg 1 or 3 antibodies above the upper limit of normal (ULN).
  - c. History of at least one positive tissue-based test (eg, biopsy, direct immunofluorescence [DIF]).
4. Active disease defined as lesions lasting  $> 2$  weeks, and 3 active lesions in skin or mucosa or 2 active lesions with at least one being a skin lesion  $> 1$  cm diameter:
  - a. If treated with rituximab or other anti-CD20 mAb, last dose  $> 12$  months prior to screening.
  - b. If being treated with other immunosuppressants (ie, azathioprine, mycophenolate mofetil, methotrexate, dapsone, cyclosporine, tacrolimus, sirolimus, or low-dose cyclophosphamide [ $\leq 100$  mg/day]), dose must be stable, defined as  $< 25\%$  change in dose, for 4 weeks prior to screening.
  - c. On stable dose of corticosteroids, defined as  $\leq 1$  mg/kg of prednisone or equivalent and may not be increased by more than 50% in the 2 weeks prior to screening.

- d. Allowed topical therapies for pemphigus lesions upon entering the study include petroleum jelly or Aquaphor® for the skin or chlorhexidine for the mouth.
  - e. Stable use of topical low strength hydrocortisone ( $\leq 1\%$ ), tacrolimus, sirolimus, or pimecrolimus for lesions contributing  $< 10\%$  of the PDAI total activity score for the 4 weeks prior to screening is allowed. Stable use of dexamethasone elixir solution (swish and spit only) for oral lesions for the 4 weeks prior to screening is allowed.
  - f. If not on regular corticosteroids, no pulse corticosteroids are allowed in the 2 weeks prior to screening.
5. Body mass index (BMI)  $> 18.5$  kg/m^2.
  6. Has a negative pregnancy test documented prior to the first dose of study drug (for women of childbearing potential).
  7. Females of childbearing potential must agree to be abstinent or else use any two of the following medically acceptable forms of contraception ( $< 1\%$  per year failure rate) from the screening period through the final study visit: oral contraceptive, condom with or without spermicidal jelly, diaphragm or cervical cap with spermicidal jelly, or intrauterine device (IUD). A female whose male partner has had a vasectomy must agree to use one additional form of medically acceptable contraception.
  8. Females of non-childbearing potential, defined as surgically sterile (status post hysterectomy, bilateral oophorectomy, or bilateral tubal ligation) or post-menopausal for at least 12 months do not require contraception during the study.
  9. Males with female partners of childbearing potential, including males who are surgically sterile (post vasectomy), must agree to be abstinent or else use a medically acceptable form of contraception from the screening period through 60 days after the final study visit.
  10. A PDAI total activity score of  $> 4$  at screening.

### 6.3 Exclusion Criteria

A subject who meets any of the following criteria is ineligible for the study:

1. Subject unable or unwilling to comply with the protocol.
2. Active non-hematologic malignancy or history of non-hematologic malignancy in the 3 years prior to screening (exclusive of non-melanoma skin cancer and cervical cancer in situ).
3. Positive for human immunodeficiency virus (HIV) or hepatitis C antibody.
4. Positive for hepatitis B surface antigen.
5. Active infection or history of recurrent infections.
6. IVIG treatment within 30 days of screening.
7. Received any cytotoxic (other than azathioprine) or any non-anti-CD20 mAb therapy in the 3 months prior to screening.
8. Any exposure to an investigational drug or device within the 30 days prior to screening.
9. Plasmapheresis or immunoadsorption within 30 days of screening.
10. Cellular therapy, including chimeric antigen receptor and T-cell (CAR-T), at any time prior to screening.
11. Use of any systemic or topical immunosuppressive drugs within 3 months of screening not including dose allowed by the inclusion criteria.
12. Serum total IgG  $< 600$  mg/dL.

13. Subject has any current medical condition that, in the opinion of the Investigator, may compromise their safety or compliance, preclude successful conduct of the study, or interfere with interpretation of the results (eg, a significant pre-existing illness or other major comorbidity that the Investigator considers may confound the interpretation of the study results).
14. Any vaccination within 2 weeks of screening.

